5.4 Screen Failures

A subject who has signed a consent form, has been assigned a screening number, but is not randomized is classified as a screen failure. Subject number, demography and reason for screen failure will be collected. Subjects who fail their first screening attempt may be rescreened again (i.e., up to two screenings total) and may be enrolled if they are found to meet all inclusion and none of the exclusion criteria at SV2. Rescreening follows a subject, not a specific wound, so subjects cannot be screened > 2 times for different wounds. Anytime a subject screen fails and later rescreens (outside of the original 2 weeks screening window), they must be re-consented for the study.

Confidential Page 34 of 73

6 Standard of Care Study Treatment Primary Dressing

6.1 Method for Assigning Eligible Subjects to Treatment

Eligible subjects will be assigned to one of the treatment groups based on a randomization schedule. Details of the randomization are provided in the statistical analysis section.

6.2 MIRRAGEN™ Product Information (provided from IFU)

Product Description

The MIRRAGEN™ Advanced Wound Matrix is a wound dressing solely composed of biocompatible and resorbable borate-based bioactive glass fibers and particles. It is a flexible and moldable advanced wound dressing that can be easily customized to fit the wound bed. The fiber structure of the MIRRAGEN™ Advanced Wound Matrix allows it to absorb fluid from the wound and facilitate natural wound healing. The bioabsorbable material used in the MIRRAGEN™ Advanced Wound Matrix is a borate glass specially designed for medical applications. The material is biocompatible and will eventually be fully absorbed at the wound site. This resorption process is initiated by the exposure of the dressing to fluid at the wound site.

Indications for Use

The MIRRAGEN™ Advanced Wound Matrix is intended for use in the management of wounds. Wound types include:

- Partial and full-thickness wounds
- Pressure ulcers
- Venous ulcers
- Diabetic ulcers
- Chronic vascular ulcers
- Tunneled/undermined wounds
- Surgical wounds (donor sites/grafts, post-Mohs surgery, post laser surgery, Podiatric, wound dehiscence)
- Trauma wounds (abrasions, lacerations, first- and second-degree burns, skin tears)
- Draining wounds

The product is designed for single patient/single treatment use only. DO NOT reuse.

Warnings MIRRAGEN™ Advanced Wound Matrix is sterile only if the packaging is unopened and undamaged. DO NOT re-sterilize. DO NOT use expired product.

Precautions MIRRAGEN™ Advanced Wound Matrix dressings are intended to be used under the supervision of a healthcare professional.

Adverse Reactions Possible adverse reactions may include local irritation, swelling, inflammation, excessive redness, or pain.

Contraindications The use the MIRRAGEN™ Advanced Wound Matrix should be discontinued if any adverse reactions are observed.

Confidential Page 35 of 73

How Supplied MIRRAGEN™ Advanced Wound Matrix is supplied sterile. The dressing is packaged in a two-piece disposable tray that is sealed in a foil pouch.

Instructions for Use The MIRRAGEN™ Advanced Wound Matrix is sterile. Use aseptic techniques when applying the dressing.

- 1. Prepare the wound bed using standard wound cleaning and debridement procedures.
- 2. Dry the area surrounding the wound.
- 3. Cut or shape the MIRRAGEN™ Advanced Wound Matrix dressing to fit the size of the wound bed. Place the dressing directly in contact with the wound, ensuring the entire wound area and wound margins are covered.
- 4. If applying MIRRAGEN™ Advanced Wound Matrix to a dry wound, moisten the dressing with sterile saline to aid in maintaining a moist wound environment.
- 5. Place a suitable secondary dressing over the MIRRAGEN™ Advanced Wound Matrix to manage the wound environment and protect the wound area. The secondary dressing should completely cover the MIRRAGEN™ dressing.
- 6. Dressing changes are conducted according to standard wound care practices every 3 to 7days. As healing occurs, new tissue may grow into the MIRRAGEN™ Advanced Wound Matrix. Do not forcibly remove or debride areas of the MIRRAGEN™ dressing that are embedded or adhered to the wound site. The MIRRAGEN™ dressing is 100% bioabsorbable and will eventually be absorbed at the wound site.
- 7. Loose sections of the MIRRAGEN™ Advanced Wound Matrix may be removed. Apply additional MIRRAGEN™ dressing to fill and cover the wound. Moisten the dressing with sterile saline, as needed.
- 8. Secondary dressings should also be replaced at each dressing change.
- 9. Heavy exuding wounds may require more frequent dressing changes.

Storage Do not expose to excessive heat and humidity.

Shelf-life Refer to pouch label.

Sterilization This device has been sterilized with gamma irradiation

Manufactured and Distributed by:

ETS Wound Care, LLC [name] USA P h o n e + 1 - [contact] Fax: + 1 - [contact] [contact] www.etswoundcare.com

6.3 FIBRACOL™ Product Information (provided from IFU)

Confidential Page 36 of 73

Product Description

FIBRACOL™ Plus Collagen Wound Dressing with Alginate is an advanced wound care device composed of collagen and calcium alginate fibers. FIBRACOL™ Plus dressing contains 80% more collagen than our traditional FIBRACOL™ Dressing. Its unique combination of natural biopolymers created by a patented process combines the structural support of collagen and the gel forming properties of alginates into a sterile, soft, absorbent, conformable topical wound dressing. In the presence of wound fluid FIBRACOL™ Plus dressing maintains a physiologically moist microenvironment at the wound surface that is conducive to granulation tissue formation, epithelialization, and enables healing to proceed at a rapid rate. FIBRACOL™ Plus dressing is versatile as a primary wound dressing, it can be cut to the exact size of the

wound, multi-layered for the management of deep wounds and used in combination with either a semi-occlusive or non-occlusive secondary dressing.

Indications

FIBRACOL™ Plus dressing is indicated for the management of exuding wounds including:

- Full-thickness and partial-thickness wounds Pressure ulcers
- Venous ulcers
- Ulcers caused by mixed vascular etiologies Diabetic ulcers
- Second-degree burns
- Donor sites and other bleeding surface wounds Abrasions
- Traumatic wounds healing by secondary intention Dehisced surgical incisions

Precautions

FIBRACOL™ Plus dressing may be used when visible signs of infection are present in the wound area only when proper medical treatment addresses the underlying cause. FIBRACOL™ Plus dressing may be used under compression therapy with healthcare professional supervision.

Contraindications

FIBRACOL™ Plus dressing is not indicated for wounds with active vasculitis, third-degree burns, or patients with known sensitivity to collagen or alginates.

Adverse Reactions

Confidential Page 37 of 73

FIBRACOL™ Plus dressing should not be used on patients with known sensitivities to collagen or alginates. Discontinue use if signs of sensitivity appear.

Directions for Use

Debride when necessary and irrigate the wound site with normal saline solution. Remove excess solution from surrounding skin. For heavily exuding wounds, apply to wound bed directly. For wounds with minimal exudate, apply to moistened wound bed; this will initiate the gel forming process.

Pack deep wounds loosely. The dressing can be cut to size with sterile scissors. The amount of FIBRACOL™ Plus dressing to be used depends on the size of the wound and the amount of exudate.

FIBRACOL™ Plus dressing may be covered with either a non-occlusive secondary dressing and fixed to the skin with a non-irritating tape or a semi-occlusive dressing. Reapply FIBRACOL™ Plus dressing when the secondary dressing has reached its absorbent capacity or whenever good wound care practice dictates that the dressing should be changed. A heavily exuding wound may require daily or twice daily dressing changes. More moderately exuding wounds will require less frequent changes

Following the initial application, irrigate the wound with saline solution. Reapply FIBRACOL™ Plus dressing as previously instructed.

Dressing Removal

After gently removing the secondary dressing, lift any FIBRACOL™ Plus dressing that has not formed a gel and discard. Using normal saline, gently irrigate the wound to remove any residual gel.

Do not re-use.

Do not re-sterilize.

Do not use it if the package is damaged.

The use by date of this product is printed on the packaging.

Caution: Federal Law (USA) restricts this device to sale by or on the order of a properly licensed healthcare practitioner.

Confidential Page 38 of 73

7 Standard of Care, Concomitant Medications, Excluded/Allowed Therapies/Medications and Allowed Dressings

Beginning at the screening visit, ALL subjects must have their index ulcer managed using the SOC procedures noted below.

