4.2 Phase 2: Treatment

The Treatment Phase (up to 13 weeks) begins with a series of assessments designed to confirm the subject's continued eligibility. Investigators will debride the ulcer, in accordance with SOC if required. Subjects whose ulcers continue to meet eligibility criteria will then be randomized to one of two groups: (1) SOC with MIRRAGEN™ primary dressing or (2) SOC with FIBRACOL™ primary dressing. Additionally for the most compassionate care subjects in either group whose ulcers have demonstrated wound area reduction by less than 50% at week 7 of treatment will be considered a treatment failure and will be permitted to obtain additional outside treatment and thus will be exited from the study.

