4.4.2 Exclusion Criteria

Potential subjects meeting any of the following criteria will be excluded from enrollment and subsequent randomization:

Confidential Page 20 of 73

- 1. A subject known to have a life expectancy of < 6 months is excluded.
- 2. If the target ulcer is infected or if there is cellulitis in the surrounding skin, the subject is excluded.
- 3. Presence of osteomyelitis or exposed bone, probes to bone or joint capsule on investigator's exam or radiographic evidence.
- 4. A potential subject cannot have an infection in the target ulcer or in a remote location that requires systemic antibiotic therapy.
- A subject receiving immunosuppressants (including systemic corticosteroids at doses greater than 10 mg of Prednisone per day or equivalent) or cytotoxic chemotherapy is excluded.
- 6. The topical application of steroids to the ulcer surface within one month of initial screening is not permitted.
- 7. A subject with a previous partial amputation on the affected foot is excluded if the resulting deformity impedes proper offloading of the target ulcer.
- 8. If a subject has a glycated hemoglobin (HbA1c) greater than or equal to 12% taken at or within 3 months of the initial screening visit he/she is excluded.
- 9. If a subject has a serum creatinine ≥ 3.0mg/dL within 6 months of randomization he/she is excluded.
- 10. The subject is excluded if the surface area measurement of the target ulcer has reduced in size by more than 30% in the 2 weeks prior to the initial screening during the 2-week screening phase: the 2 weeks from the initial screening visit (SV1) to the TV1/randomization visit during which time the subject received SOC.
- 11. A Subject with an acute Charcot foot, or an inactive Charcot foot, that impedes proper offloading of the target ulcer is excluded.
- 12. Women who are pregnant or considering becoming pregnant within the next 6 months are excluded.
- 13. A potential subject with end stage renal disease requiring dialysis is excluded.
- 14. A subject who participated in a clinical trial involving treatment with an investigational product within the previous 30 days is excluded.
- 15. A subject who, in the opinion of the Investigator, has a medical or psychological condition that may interfere with study assessments is excluded.
- 16. A Subject treated with hyperbaric oxygen therapy or a Cellular and/or Tissue Product (CTP) in the 30 days prior to the initial screening visit is excluded.

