8.2 Assessment of Eligibility

At each visit during the Screening Period, the Investigator must assess a subject's continued suitability and eligibility for the study, especially with regard to the Inclusion and Exclusion criteria. If the subject is no longer suitable or eligible for the study, the subject will be considered a screen failure. Screen failure subjects may be re-entered into the study at a later time and re-screened.

Further, a panel of three board-certified plastic surgeons will review each wound, as well as inclusion/exclusion criteria, in a blinded fashion to ensure that randomizations are appropriate. The review will occur between SV2 and the day of randomization. The plastic surgeon will provide correspondence to the trial manager that the subject is appropriate for randomization, prior to the site being able to randomize the patient.

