8.4.2 Medical History

A medical history will be recorded during the Screening Period and will include:

- All ongoing medical conditions
- All previously resolved medical conditions related to diabetes or foot ulceration or which are relevant in the opinion of the Investigator

Events that emerge prior to the randomization visit will be recorded in the medical history and not as Adverse Events. Aside from being used to determine subject eligibility, this information will permit the Investigator to record the nature, duration and severity of any ongoing baseline medical conditions that occur prior to randomization

Medical histories will be recorded using the body system categories outlined below:

Cardiovascular

Respiratory

Gastrointestinal

Renal

Hepatic

Neurological

Endocrine

Lymphatic

Hematologic

Immunologic

Dermatologic

Psychiatric

Genitourinary

Other

DFU History

For each relevant history, the following will be documented:

- Disease/disorder/condition
- Date of diagnosis
- History status (resolved or ongoing)

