8.4.3 Foot Ulcer History

Duration of the current DFU

Note: "Duration" is defined as the length of time that the index ulcer has been open at this location since the last time it was fully closed.

- Current offloading system used for the DFU (if any) and length of time that this has been used
- Prior treatments that have been used on the DFU for up to 1-year
- Age when the subject developed his/her first DFU
- Total number of previous DFUs
- Location of the current DFU

Note: "Index ulcer location" is defined by the ulcer being on the left or right foot, by the location of the ulcer on the foot, dorsal or plantar, toe (which toe), forefoot, midfoot, hind foot, ankle heel and by the positioning of the ulcer as lateral, medial, dorsal, or plantar located.

- Number of additional DFUs and location of each present at the screening visits
- History of DFU recurrence

Confidential Page 43 of 73

Note: "Recurrence" is defined as the re-opening of the index ulcer after complete healing.

- History of any amputations in the study foot and contralateral foot or leg
- History of any significant foot deformities, dermatological abnormalities, fungal lesions, or other findings.

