14.1 Recording and Collection of Data

The primary source document for this study will be the subject's medical record. If separate research records are maintained by Investigators, the medical record and the research records will be considered the source documents for the purposes of auditing the study.

Applicable source data will be manually transcribed to the approved CRF. The Investigator is ultimately responsible for the accuracy of the data transcribed on the forms. All source documents and CRFs will be completed as soon as possible after the subject's visit.

The Investigator will review CRFs to indicate that, to his/her knowledge, they are complete and accurate. If further changes are made after this, the Investigator will need to again sign the Investigator signature page. Designated source documents will be signed and dated by the appropriate study personnel. The Investigator must agree to complete and maintain source documents and CRFs for each subject participating in the study.

All research data will be entered, either electronically or manually, into a computerized database, designed in accordance with the clinical data manager.

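### The protocol's own contraindication to FIBRACOL for known collagen or alginate sensitivity is not carried into any eligibility criterion

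*Combined protocol and SAP*

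**What the plan says.** Section 6.3 reproduces the product information for the comparator and restricts its use twice. Under Contraindications: "FIBRACOL™ Plus dressing is not indicated for wounds with active vasculitis, third-degree burns, or patients with known sensitivity to collagen or alginates". Under Adverse Reactions: "FIBRACOL™ Plus dressing should not be used on patients with known sensitivities to collagen or alginates", followed by an instruction to stop using the dressing if sensitivity shows itself.

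Eligibility is set by 12 inclusion and 16 exclusion criteria, printed in the synopsis and again in section 4.4. The exclusion list opens: "Potential subjects meeting any of the following criteria will be excluded from enrollment and subsequent randomization". Entry to the treatment phase (section 4.2) then depends on those criteria: "Subjects whose ulcers continue to meet eligibility criteria will then be randomized to one of two groups". One of the two groups is FIBRACOL.

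Other provisions bear on the point:

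- Section 8.2 asks the investigator to judge suitability at each screening visit: "If the subject is no longer suitable or eligible for the study, the subject will be considered a screen failure".
- Section 8.4.2 collects all ongoing conditions: "Medical histories will be recorded using the body system categories outlined below". The categories include immunologic and dermatologic.
- Section 8.4.3 asks for "Prior treatments that have been used on the DFU for up to 1-year".
- Section 14.1 makes the medical record the primary source document.
- Sections 4.1, 4.5.2 and 8.2 require three plastic surgeons to review each wound and the eligibility criteria before a site may randomize.
- Exclusion 15 gives the investigator discretion over conditions that could interfere with study assessments.
- Section 5.3 lets the investigator discontinue a subject when medically necessary.
- Section 5.2 counts a withdrawn subject as a treatment failure, while section 9.2 provides for imputation of withdrawn subjects in the ITT analysis.

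**The concern.** The protocol tells the investigator not to use the comparator on a certain kind of patient, yet the list that decides who is randomized does not exclude that patient. A site that applies the criteria exactly as written can allocate a subject to a dressing that the same document says should not be used on that subject.

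What is at stake is first the subject's safety. Second, if the sensitivity is recognized only after allocation to FIBRACOL, the investigator must either depart from the allocated dressing or withdraw the subject. This can happen in one arm only, because the MIRRAGEN information in section 6.2 lists no sensitivity that bars use in advance; it says to discontinue if adverse reactions are seen. An exclusion applied before randomization avoids the problem in both arms alike.

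**Working it through.** **Step 1: compare the texts.** The contraindication has two parts that could apply to a diabetic foot ulcer: known sensitivity to collagen or alginates, and active vasculitis of the wound. Third-degree burns are not relevant to the target wound. Each part is checked against every place that could stop the subject before randomization.

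| Place | Names collagen or alginate sensitivity? |
|---|---|
| Inclusions 1–12, synopsis and 4.4.1 | No (0 of 12) |
| Exclusions 1–16, synopsis and 4.4.2 | No (0 of 16) |
| Exclusion 15 | No; limited to interference with assessments |
| SV1, SV2 and TV1 procedures (4.5.2, 4.5.3.1) | No allergy or sensitivity item |
| Three-surgeon panel | No; reviews the wound and the same criteria |
| Suitability check (8.2) | No; general judgement |
| Medical and ulcer history (8.4.2, 8.4.3) | No; could bring it to light |

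None of these names active vasculitis either.

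**Step 2: chance of receiving the contraindicated dressing.** Inputs: 120 subjects per arm, 240 in all (section 9.2), equal allocation. Let K be the number of known-sensitive subjects randomized. The documents give no value, so K = 1 to 3 is an assumption for illustration. The chance that at least one is allocated to FIBRACOL is:

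- K = 1: 120/240 = 0.500
- K = 2: 1 − (120×119)/(240×239) = 0.751
- K = 3: 1 − (120×119×118)/(240×239×238) = 0.877

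**Step 3: effect on the primary comparison.** Let k be the number of such subjects who fall in the FIBRACOL arm, are withdrawn and are scored as failures under section 5.2. With the planned control proportion of 0.35:

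- Average fall in the FIBRACOL healing proportion per subject: 0.35/120 = 0.29 percentage points.
- Largest fall, if the subject would have healed: 1/120 = 0.83 points.
- Planned difference: 0.70 − 0.35 = 35 points.

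The two-sided rejection rate with no true effect comes from exact enumeration: MIRRAGEN Bin(120, 0.35) against FIBRACOL Bin(120 − k, 0.35) healed of 120, pooled Z-test, nominal 0.05, no continuity correction.

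| k | Null rejection rate | Probability of k when K = 3 |
|---|---|---|
| 0 | 5.043% | 0.1234 |
| 1 | 5.032% | 0.3766 |
| 2 | 5.073% | 0.3766 |
| 3 | 5.167% | 0.1234 |

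Averaged over allocation for K = 3:

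0.1234×5.043 + 0.3766×5.032 + 0.3766×5.073 + 0.1234×5.167 = 5.07%, against 5.04% with no such subject.

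Power at 0.70 against 0.35 is above 0.999 for k = 0 to 3.

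**The case against.** The strongest reply is that the problem concerns a *known* sensitivity, and the investigator holds a protocol that prints the restriction twice in the section describing the dressing. A medical history and the prior treatments of the ulcer are taken, and an unsuitable subject is screen-failed under section 8.2. The surgeon panel must agree before the site can randomize. If a reaction occurs, section 6.3 says to stop using the dressing and section 5.3 allows discontinuation. On this view the point is a drafting preference.

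Most of this stands, and it keeps the severity low. It does not close the gap. Section 6.3 governs use of the dressing and does not bar randomization. The panel checks a list on which the item does not appear. Ulcer history covers treatments of this ulcer for up to a year and need not reveal a reaction to a dressing used elsewhere or earlier. Stopping when signs appear acts only after exposure.

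The vasculitis part is weaker. The target must be a diabetic foot ulcer with documented adequate circulation, and subjects on immunosuppressants are excluded, so few such wounds are likely to reach randomization.

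A reader might also infer that failures confined to the FIBRACOL arm bias the primary result in favour of MIRRAGEN. The documents do not support a material effect. The 5.17% rate needs all three illustrative subjects to fall in the FIBRACOL arm (probability 0.12) and all to be withdrawn. Scoring them as failures is itself not settled, since section 9.2 provides for imputation. Nor do the documents support reading the protocol as having no safeguard at all.

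**Conclusion.** The gap is real and small. No inclusion or exclusion criterion carries over the comparator's contraindication, so a known-sensitive subject can satisfy the written criteria and face a 50% chance of FIBRACOL. The general safeguards make this less likely but leave it to individual judgement at each site.

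The reason to act is subject safety and consistency within the protocol. The effect on the primary analysis is negligible: about 0.03 percentage points on the null rejection rate (5.07 − 5.04) with three such subjects. That figure assumes equal allocation, a healing proportion of 0.35 in both arms, a single test at nominal 0.05, withdrawal of every such subject in the FIBRACOL arm, and failure scoring under section 5.2 in place of imputation under section 9.2. The number of such subjects is unknown from the documents, and no prevalence is claimed. This is a cheap improvement.

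**What to change.** Add one exclusion to the synopsis and to section 4.4.2: known sensitivity to collagen or alginates. Active vasculitis of the target ulcer can share the line as a minor addition, since section 6.3 lists it in the same sentence. Add a matching item to the SV1 medical history (sections 4.5.2 and 8.4.2), so that it is confirmed for every subject before randomization, whichever arm follows. Once it is a numbered criterion, the surgeon panel's review covers it without further change.

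The cost is one line of text and one question in a history already taken. The downside is the loss of a very few otherwise eligible subjects, who should not receive the comparator in any case. Their number cannot be given from the documents.
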